7.4 Reporting Procedures

The primary investigator will be responsible for determining the severity and whether any AE or SAE is study related.

Severity of Event

For adverse events (AEs), the following guidelines will be used to describe severity.

- Mild – Events require minimal or no treatment and do not interfere with the participant's daily activities.
- Moderate – Events result in a low level of inconvenience or concern with the therapeutic measures. Moderate events may cause some interference with functioning.
- Severe – Events interrupt a participant's usual daily activity and may require systemic drug therapy or other treatment. Severe events are usually potentially life-threatening or incapacitating. Of note, the term "severe" does not necessarily equate to "serious".

These terms should match those collected on the Adverse Event Form.

Relationship To Study Intervention

Given the nature of the intervention, a binary assessment (related/not related) will be used. No AE's or SAE's are expected based upon the study intervention. Hospitalizations and ED visits are secondary outcomes in the study and not considered adverse events.

AEs for this study include: Mild inconvenience due to the time taken for the intervention.

SAEs for this study include: Given the nature of the participant population based on age and comorbidities, death can reasonably be expected (unrelated to the intervention) in some PLWD.

7.5 Follow-up for Adverse Events

The occurrence of an adverse event (AE) or serious adverse event (SAE) may come to the attention of study personnel during visits with the ODC or study team review of the medical record.

We will distinguish between alerts and adverse events as developed by the NIH REACH initiative. Alerts refer to events occurring independently of the study and place the PLWD or care partner at risk. These could include a care partner medical emergency, PLWD driving, aggression in the dyad, suicidal ideation in a care partner or PLWD, etc. The Project Manager will keep a running record of alerts and dates of resolution. We will seek resolution of an alert within 48 hours of being notified of such and define resolution as the participant being contacted and informed of actions to resolve the presenting issue. Alert forms will be reviewed by [name] weekly during research administration meetings. Adverse events include hospitalization, ED visit, nursing home placement or death of a caregiver or PLWD. There are two levels of monitoring of adverse events. For AEs attributed to the study/intervention, notification of the PI, IRB, Safety Officer (SO) and NIA occurs within 24 to 48 hours of identification of the event, as per the DSMP and as noted in Section 7.7 below. For AEs not attributed to the study/intervention, the first level of monitoring occurs on a weekly basis and involves the following; a) the PI are notified of all non-emergency events at staff meetings with project directors at their respective sites; b) events are reviewed at weekly interviewer meetings at respective sites to assure that each has been managed appropriately and follow-up and resolution obtained); c) all events will be entered in a secure on-line data management system developed, and monitored at DU. The second level of review involves generating aggregate data reports that are provided to both PIs and SO twice yearly for review (or more frequently if they so choose). Data entry and an aggregate review facilitate a double check that events are resolved and assist in monitoring of the trial. Resolution of events is defined as the participant having been contacted and informed of actions to resolve the presenting issue.

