7.3 Adverse Events and Serious Adverse Events

Adverse Event (AE): Any untoward or unfavorable medical occurrence in a clinical research study participant, including any abnormal sign (e.g. abnormal physical exam or laboratory finding), symptom, or disease, temporally associated with the participants' involvement in the research, whether or not considered related to participation in the research.

Serious Adverse Event (SAE): Any adverse event that:

- Results in death
- Is life threatening, or places the participant at immediate risk of death from the event as it occurred
- Causes persistent or significant disability or incapacity
- Results in congenital anomalies or birth defects
- Is another condition which investigators judge to represent significant hazards

No AE's or SAE's are expected based upon the study intervention. Hospitalizations and ED visits are secondary outcomes in the study and not considered adverse events. However, we will collect data on such events from the medical chart and caregiver report during visits and report them as needed.

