- All **unanticipated problems (UPs)** will be reported to the IMPACT Collaboratory Regulatory and Data Team Leader ([name]), Advarra IRB, NIA IMPACT Collaboratory PO ([name]), and the IMPACT Collaboratory project's Safety Officer (SO) within 48 hours of the study's knowledge of the event.

- The summaries of all previously reported unexpected and related SAEs, deaths, and UPs, *as well as* all other SAEs and AEs will be reported to IMPACT Collaboratory Regulatory and Data Team Lead ([name]), Advarra IRB, NIA IMPACT Collaboratory PO ([name]), and the IMPACT Collaboratory project's Safety Officer (SO) at a minimum every 6 months, or at a frequency requested by the IMPACT Collaboratory project's Safety Officer (SO) or NIA IMPACT Collaboratory PO.

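### Section 7.5 presumes that alerts such as suicidal ideation and dyad aggression are independent of the study, which conflicts with the timing-based AE definition in 7.3 and leaves them no stated route to grading, attribution or the Safety Officer

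*Combined protocol and SAP*

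**What the plan says.** Section 7.3 defines an adverse event as an untoward medical occurrence, symptoms included, that is "temporally associated with the participants' involvement in the research, whether or not considered related to participation in the research". Section 7.4 gives the investigator the task of judging severity and relatedness for AEs and SAEs.

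Section 7.5 then sets up a second class: "We will distinguish between alerts and adverse events as developed by the NIH REACH initiative". It continues: "Alerts refer to events occurring independently of the study and place the PLWD or care partner at risk". Four examples are offered as possibilities: a medical emergency in the care partner, driving by the person with dementia, and "aggression in the dyad, suicidal ideation in a care partner or PLWD, etc".

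For handling, "The Project Manager will keep a running record of alerts and dates of resolution". Resolution is sought within 48 hours, and the forms are reviewed "weekly during research administration meetings". For alerts, the plan will "define resolution as the participant being contacted and informed of actions to resolve the presenting issue". The end of 7.5 gives events under AE monitoring a resolution definition of the same content.

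The AE list in 7.5 names hospitalization, ED visits, nursing home placement and death. Suicidal ideation and aggression are not in it. Section 7.7 covers SAEs, deaths and unanticipated problems, and adds that "all other SAEs and AEs will be reported" at least every 6 months to recipients who include the Safety Officer. It does not mention alerts.

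**The concern.** Under 7.3, whether an event is related to the study has no bearing on whether it is an AE; that judgement comes afterwards, under 7.4. Under 7.5, an event classed as an alert is taken to be independent of the study before anyone has assessed it, and it sits in a class described as distinct from AEs.

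This matters for the kinds of event listed. Section 2.1 names aggression among the behavioral symptoms that care partners manage, and section 5.1 has the ODC instruct care partners in strategies for such symptoms. A change in aggression, or distress in a care partner, after a strategy is tried is something a safety review would want to see and attribute. The consent waiver in 11.2 rests on minimal risk, and the pilot is meant to inform a full-scale trial, so its safety summaries should be able to show such events if they occur.

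The definition of resolution adds a second difficulty. If an event counts as resolved once the participant has been reached and told what will be done, a continuing event can be logged as closed.

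**Working it through.** No arithmetic applies: the plan gives no figure on this point and the conclusion depends on none. The check compares sections 7.3 to 7.7.

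**Step 1: do the alert examples meet the 7.3 definition?** The test in 7.3 is an untoward medical occurrence, including a symptom, in a participant, linked in time to participation.

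- Care partner medical emergency: meets it plainly. Care partners are enrolled as half of each dyad, and 7.5 itself counts a caregiver's death as an AE.
- Suicidal ideation in either member of the dyad: meets it as a symptom.
- Aggression in the dyad: arguably meets it as a behavioral symptom, although it may be the pre-existing behavior that led to referral.
- Driving by the person with dementia: a hazard rather than a medical occurrence; it does not obviously meet it.

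So of four examples, two fit 7.3, one arguably does, and one probably does not.

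**Step 2: what is written for each class?**

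| Step | Handled only as an alert | Handled as an AE |
|---|---|---|
| Record | Project Manager's log (7.5) | Online data system, for AEs not attributed to the study (7.5) |
| Regular review | Weekly; reviewer's role not visible because the name is removed (7.5) | Weekly, for AEs not attributed to the study (7.5) |
| Severity and relatedness | None stated | Investigator (7.4) |
| Prompt notice to Safety Officer | None stated | 24 to 48 hours if attributed to the study (7.5); 48 hours if serious and unexpected, 24 hours for a death (7.7) |
| Periodic report to Safety Officer | None stated | Aggregate report twice yearly (7.5); summary at least every 6 months (7.7) |
| Rule for moving between classes | None stated | None stated |
| Meaning of resolution | Participant reached and told of actions | Same |

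**Step 3: follow one event through.** Suppose a care partner reports suicidal ideation at a follow-up call. Under 7.3 it is an AE, graded and attributed under 7.4 and summarized under 7.7. Under 7.5 it is a named example of an alert, logged, acted on within 48 hours and reviewed weekly. A site that follows 7.5 alone has complied with 7.5 but has omitted an event that 7.3 requires as an AE. No section says which rule governs, who judges independence, or when both entries are needed.

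**Step 4: resolution.** The 7.5 definition refers to contact and information. It holds no state for an event that is ongoing, and it cannot be applied to a participant who has died. The twice-yearly review is described in 7.5 as a double check that events are resolved; on this definition, the recorded field can confirm only that contact took place.

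**The case against.** The strongest reply is that 7.5 is silent on these steps and does not forbid them. The examples are introduced as things alerts could include, and independence can be read as a condition to be met, so that an event thought to follow a DICE strategy would not be an alert at all. Nothing bars entering one event both as an alert and as an AE. Section 6.1 schedules adverse events at all seven visits. The 0 to 4 behavior score is repeated at 2 weeks (5.1), so aggression would be rescored where it is the target behavior. An alert that leads to hospitalization, an ED visit, nursing home placement or death is an AE under 7.5. Unexpected SAEs, unanticipated problems and deaths go to the Safety Officer, who also oversees all safety monitoring (7.6). Weekly meetings check that AEs not attributed to the study were managed and followed up, which is more than a call. The alert scheme follows an outside model and 7.5 refers to a separate monitoring plan; neither is available here.

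Most of this stands, and it rules out a stronger reading. A reader might infer that these events are never assessed, that they never reach the Safety Officer, or that the pilot is bound to report no related events of these kinds. The documents do not support that: several routes remain open. Nor do they support ranking worsened aggression as the likeliest harm, or treating the minimal-risk statement as circular. That statement is a prior justification for the consent waiver and for not having a DSMB, not a planned conclusion from AE counts.

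The reply does not remove the conflict. If independence is a condition, 7.5 does not say who judges it. If dual entry is allowed, no rule tells a site to make it. A separate log for hazards such as driving is a legitimate choice, but it does not require alerts to be presumed unrelated.

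**Conclusion.** The conflict is real but limited. Section 7.5 presumes alerts to be independent of the study, while 7.3 makes AE status independent of relatedness. For events handled only as alerts, no grading, attribution, conversion to AE or Safety Officer report is stated. Events meeting 7.3 can therefore be left out of the safety summaries unless a site also enters them as AEs or they qualify as SAEs, deaths or unanticipated problems. Separately, and however the alert definition is read, resolution of both alerts and AEs is recorded as an action and not as the event's outcome.

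The size cannot be given as a count, because the documents contain no rate for any of these events. It can be given by kind: two of the four named examples plainly meet 7.3 and a third arguably does. The conclusion assumes that care partners are participants for the purpose of 7.3, as dyad enrollment and the caregiver events in the 7.5 AE list imply, and that suicidal ideation counts as a symptom. It assumes nothing about the weekly reviewer's role, which is hidden by name removal. The change should be made, but it does not affect the design or the sample size.

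**What to change.** Reconcile 7.5 with 7.3 as follows.

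1. In 7.5, delete the clause that makes independence from the study part of the alert definition, and state that an alert is a handling flag that prompts action, not a class of event separate from AEs.
2. State that any alert meeting the 7.3 definition is also entered as an AE or SAE, graded and attributed by the investigator under 7.4, and reported under 7.7.
3. Add counts of alerts by type to the periodic summaries in 7.7, so that the Safety Officer sees those not entered as AEs as well.
4. Record the date of participant contact as an action, and record the event's outcome in its own field: resolved, ongoing, fatal or unknown.

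The cost is wording in 7.5 and 7.7 and one added field on the adverse event form. The downside is some additional AE entries for events already in the alert log. No change to the intervention, the visit schedule or the sample size is involved.

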7.6 Safety Monitoring

Given the minimal risk nature of the study embedded in usual care, NIA determined that a DSMB is not required. Rather, the IMPACT Collaboratory Safety Officer (SO) will be appointed to evaluate all study protocols and enrollment rates to ensure conformity to human subject procedures and patient safety in the trial. The SO will also review the study design, the IRB protocols, any adverse events, and interim reports of the ongoing study. [name] will be responsible for overseeing the preparation of data and data analyses for the SO. The Principal Investigator (PI) will be responsible for ensuring participants' safety on a daily basis. In addition, the NIA IMPACT Collaboratory SO will oversee all data and safety monitoring activities for this study. The SO will act in an advisory capacity to the NIA Director to monitor participant safety, to evaluate the progress of the study, and to review procedures for maintaining the

confidentiality of data, the quality of data collection, management, and analyses. Advarra IRB will conduct the ethical review required for the protection of human subjects. NIA PO, in consultation with SO, will make a determination regarding how often data safety monitoring reporting is needed.

7.7 Reporting schedule:

- All **adverse events that are serious (SAE) and unexpected** (i.e., have not been previously reported for the study's intervention) will be reported to the IMPACT Collaboratory Regulatory and Data Team Leader ([name]), NIA IMPACT Collaboratory PO ([name]), and the IMPACT Collaboratory project's Safety Officer (SO) within 48 hours of the study's knowledge of SAE.
 - Only those adverse events that are serious (SAE), unexpected, **and related to the intervention** must also be reported to Advarra IRB. Unexpected and **unrelated** SAEs will be reported to Advarra IRB on a case-by-case basis if requested by the IMPACT Collaboratory project's Safety Officer (SO) or NIA IMPACT Collaboratory PO.

- All deaths will be reported to IMPACT Collaboratory Regulatory and Data Team Leader ([name]), NIA IMPACT Collaboratory PO ([name]), and the IMPACT Collaboratory project's Safety Officer (SO) within 24 hours of study's knowledge of death.
 - Advarra IRB does not require the specific reporting of death outside of the SAE reporting requirement above, but they will be notified on a case-by-case basis if requested by the IMPACT Collaboratory project's Safety Officer (SO) or NIA IMPACT Collaboratory PO.

- All **unanticipated problems (UPs)** will be reported to the IMPACT Collaboratory Regulatory and Data Team Leader ([name]), Advarra IRB, NIA IMPACT Collaboratory PO ([name]), and the IMPACT Collaboratory project's Safety Officer (SO) within 48 hours of the study's knowledge of the event.

- The summaries of all previously reported unexpected and related SAEs, deaths, and UPs, *as well as* all other SAEs and AEs will be reported to IMPACT Collaboratory Regulatory and Data Team Lead ([name]), Advarra IRB, NIA IMPACT Collaboratory PO ([name]), and the IMPACT Collaboratory project's Safety Officer (SO) at a minimum every 6 months, or at a frequency requested by the IMPACT Collaboratory project's Safety Officer (SO) or NIA IMPACT Collaboratory PO.

8 INTERVENTION DISCONTINUATION

As a minimal risk study embedded in primary care practices, we plan to obtain a waiver of informed consent for PLWD, care partners and clinic staff in order to reduce introduction of artificial care resources or biases wherever possible. The DICE Approach will be delivered as part of routine care. It is possible that PLWD/care partners may drop out of routine outpatient care. If this occurs, we will continue to monitor and evaluate PLWD data.

9 STATISTICAL CONSIDERATIONS

9.0 General Design Issues

The overarching goal of this proposal is to refine and pilot the application of DICE in primary care clinics by: (a) leveraging existing clinic staff to deliver DICE; and (b) using electronic resources to identify and recruit PLWD-care partner dyads based on clinically relevant and minimum inclusion/exclusion criteria. We maximize a pragmatic approach and minimize a separate study infrastructure to evaluate feasibility and acceptability in order to prepare for a larger embedded pragmatic trial (ePCT). Licensed practical nurses embedded in four primary care practices at University of California Davis (UCD), whom we will refer to as “Onsite DICE Coordinators” (ODC), will coordinate behavioral management using DICE with care partner-PLWD dyads and other clinic providers. We will accomplish this goal through the following specific aims:

Aim 1. To assess the feasibility and acceptability of the ePCT protocolized version of DICE that will guide the subsequent evaluation of the effectiveness of the intervention in a full-scale ePCT. DICE will be implemented in four large primary care clinics within the UCD Health System over a 6-month period (n=100 PLWD-care partner dyads; 25 dyads per site, allowing comparison of implementation and outcomes by site characteristics). Feasibility measures will include: 1) rate of subject enrollment (PLWD-care partner dyads); 2) number of contacts between ODCs and dyads; and 3) time requirements for ODCs implementing DICE. Acceptability will be measured by the acceptance rates of the ODC’s recommendations of strategies for BPSD (generated by use of DICE) among dyads, as well as other providers within the primary care practice. Exit interviews of participants (ODCs, other providers and care partners) will be conducted to further deepen the knowledge of intervention acceptability and implementation challenges.

Aim 2. To determine the feasibility of ascertaining and analyzing the primary (psychotropic medication use) and secondary clinical outcomes (hospitalizations, ED visits and nursing home placement of PLWDs) from the existing health system-wide electronic medical record (EMR) which will subsequently be used in a full-scale effectiveness ePCT. Clinical outcomes for PLWD participants will be measured after the 6-month DICE implementation period using the EMR and

compared to corresponding outcomes for the four participating clinics in the 6 months prior to the intervention (“historical control”; all PLWD in the four participating clinics):

2a) To determine the feasibility of measuring psychotropic medication use (primary outcome) within the EMR. Mean participant psychotropic medication use during the intervention period will be compared to historical controls (mean rate of medication use for participating clinics in the 6 months prior to the intervention).

2b) To determine the feasibility of measuring hospitalizations, ED visits and nursing home placement (secondary outcomes) using the EMR. Mean participant health care utilization during the intervention period will be compared to historical controls (mean rate in the 6 months prior to the intervention).

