4.1 Inclusion Criteria

Participants must meet all inclusion criteria to participate in the study:

DICE participants

- 1) Person living with dementia (as defined by chart diagnosis) and their care partner
- 2) Care partner age >18 as defined in the EMR
- 3) Care partner English speaking

Historical controls

- 1) Person living with dementia (as defined by chart diagnosis)

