4.3 Study Enrollment Procedures

PLWD-Care partner dyads from the 4 participating clinics will be recruited via warm handoff from a clinic provider. The ODC will then contact the care partner who is identified in the EMR as the responsible person or family member for the PLWD by telephone to discuss participation in the DICE Program. Participants will be recruited from four primary care clinics in the Primary Care Network (total of 13) at University of California Davis. Clinics have been selected for the number of PLWD seen annually by clinic social workers who are embedded in each clinic. As a minimal risk study embedded in primary care practices, we plan to obtain a waiver of informed consent for PLWD, care partners and clinic staff in order to reduce introduction of artificial care resources or biases wherever possible. There will be minimal PHI data collected.

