9.1 Sample Size and Randomization

We will examine data across 4 clinics in order to assess the feasibility of a multi-site study. We selected 25 dyads per clinic as our sample size (primary study sample- total n=100 PLWD), and their caregiver (n=100) in order to have the ability to examine feasibility measures within clinic as well as across clinic with some accuracy. For example, the degree of accuracy around an enrollment rate of 75% overall is 18% (width of the 95% confidence interval), allowing us a tighter margin of error overall. Within clinic, accuracy is larger (width of 95% confidence interval 36%), suggesting more uncertainty, but allowing us to examine clinic-specific enrollment to ensure that there is consistency across clinics.

To determine the feasibility of ascertaining and analyzing the primary (psychotropic medication use) and secondary clinical outcomes (hospitalizations, ED visits and nursing home placement of PLWDs) from the existing health system-wide electronic medical record (EMR) participants (the primary study sample of PLWD n=100) will be measured after the 6-month DICE implementation period using the EMR and compared to corresponding outcomes for the four participating clinics in the 6 months prior to the intervention (historical controls n=100); all PLWD in the four participating clinics), (N=300).

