9.5 Data Analyses

Data will be summarized with descriptive statistics to allow us to review the demographics and clinical characteristics of our enrolled participants, as well as to review implausible values. The extent of missing data will also be assessed as a key indicator of feasibility of collecting data from clinic notes and the EMR; additionally, we will ascertain whether baseline characteristics are associated with missingness in order to modify study procedures for the larger trial. Feasibility will be characterized by rate of enrollment (# enrolled/# invited to enroll), number of contacts between ODCs and dyads (summarized as averages/SDs across dyads), and time requirements (summarized as averages/SDs). We will examine these overall and by clinic, to ensure consistency across clinics. We will summarize data on medication use (binary: psychotropic use or not) for the four clinics overall prior to the study and for enrolled PLWD post-intervention and will compare them using mixed models with a logit link to analyze these pre-post data, accounting for correlation within clinic. Models will first be fitted in a crude fashion, secondarily we will include covariate adjustment as a means to inform design characteristics in the ePCT, recognizing we have limited power to make definitive conclusions from these analyses. We will similarly examine healthcare utilization (counts of hospitalizations and ED visits; binary measure of nursing home placement) once we ensure that these data are feasibly collected from the EPIC EHR.

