10.3 Data Management

The UCD study team will be responsible for data collection. Data from the clinical notes as well as outcomes will be downloaded onto a secure server. A waiver of authorization for PHI data will be completed by the study team. The Drexel CO-I will be responsible for data management and analysis of a deidentified data set that is transferred from UCD and securely stored at Drexel.

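### The historical-control rule admits people who later enroll, and the planned model names no patient-level correlation, so the 90% interval behind the second go criterion is likely too wide wherever the two sets overlap

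*Combined protocol and SAP*

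**What the plan says.** All references are to the combined protocol and SAP.

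- **Control set.** Section 9.0 (Aim 2) describes the historical control as "all PLWD in the four participating clinics" in the six months before the intervention. Section 4.1 gives one control criterion: "Person living with dementia (as defined by chart diagnosis"). The exclusions in Section 4.2 concern care-partner age and language and do not remove later enrollees.
- **Participants.** Section 4.3: "PLWD-Care partner dyads from the 4 participating clinics will be recruited via warm handoff from a clinic provider". The qualifying diagnosis in Section 4.1 is the same.
- **Numbers.** Section 9.1 gives "primary study sample- total n=100 PLWD", the same number of caregivers, and "historical controls n=100". The same sentence goes on to "all PLWD in the four participating clinics), (N=300"). Section 3 instead gives a total study sample of 100.
- **Model.** For binary psychotropic use, Section 9.5 summarises the four clinics overall before the study and the enrolled PLWD afterwards, and "will compare them using mixed models with a logit link to analyze these pre-post data, accounting for correlation within clinic".
- **Decision.** The end of Section 9.5 sets two conditions for going on to the full trial. The second compares the lower limit of a 90% interval for the pre-post change with a 25% decrease in the pre-study proportion.
- **Data handling.** Section 10.3 assigns "management and analysis of a deidentified data set that is transferred from UCD and securely stored at Drexel". Section 11.3 says that data leaving the site carry a participant identification number.

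**The concern.** A person diagnosed before the intervention and still attending one of the four clinics can supply a control-window record and then an intervention-window record. Psychotropic use some months apart in one person is likely to be positively correlated. A clinic effect cannot absorb that correlation, because it describes what clinic-mates share and not what a person shares with their own earlier record.

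If the covariance is left out, the standard error of the pre-post contrast is wrong, and with positive correlation it is too large. The nominal 90% interval then covers more than 90%. This matters more than it would for a purely descriptive pilot comparison, because Section 9.5 makes this interval a condition for proceeding. There is also a timing issue: if the two records cannot be matched after de-identification, neither the overlap nor the within-person correlation can be recovered for designing the larger trial.

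**Working it through.** **1. The plan's own total.** 100 PLWD + 100 caregivers + 100 controls = 300, which reproduces Section 9.1. No adjustment for shared people enters that sum. The plan states no interval width, pre-study proportion or overlap for the second criterion, so there is no planned precision figure to reproduce.

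**2. Inputs.**
- Participants: n2 = 100 (Section 9.1).
- Controls: n1 = 100 (Section 9.1), or all PLWD in the four clinics. The table in Section 4 gives 63 + 67 + 66 + 76 = 272. That is a preliminary 2021 count of patients over 65, not a count for the control window.
- Assumed, not in the documents: use p = 0.40 in both windows (pq = 0.24), and within-person correlation rho = 0.7 (range 0.5 to 0.8).
- Shared people, m, is also assumed:
  - All 100 participants are in the 272. With all 272 as controls, m = 100. With 100 controls drawn at random, m = 100 × 100/272 ≈ 37.
  - Only 60 participants are in the 272. With all 272 as controls, m = 60. With 100 drawn at random, m = 60 × 100/272 ≈ 22.

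**3. Formula.** For a difference in proportions (a simple approximation to the logit model):

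Var/pq = 1/n1 + 1/n2 − 2 × rho × m/(n1 × n2)

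A model with no patient term omits the last part. Excess in the standard error = √(Var without it / Var with it) − 1. The 90% half-width is 1.645 × √(0.24 × Var/pq).

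**4. Two cases in full, rho = 0.7.**
- n1 = 100, m = 22: 0.02 − 2 × 0.7 × 22/10,000 = 0.01692. √(0.02/0.01692) = 1.09.
- n1 = 272, m = 100: 0.01368 − 2 × 0.7 × 100/27,200 = 0.00853. √(0.01368/0.00853) = 1.27.

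**5. Results.**

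| Controls | Shared | Half-width, no patient covariance (points) | Half-width, with it (points) | SE too large by (rho 0.5 to 0.8) |
|---|---|---|---|---|
| 100 | 22 | 11.4 | 10.5 | 9% (6–10%) |
| 100 | 37 | 11.4 | 9.8 | 16% (11–19%) |
| 272 | 60 | 9.4 | 8.3 | 14% (9–16%) |
| 272 | 100 | 9.4 | 7.4 | 27% (17–32%) |

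Actual coverage of the nominal 90% interval is 2Φ(1.645 × ratio) − 1. That is about 93% in the first row (ratio 1.09) and 96% in the last (ratio 1.27).

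**6. Other assumptions.** With pre-study use of 30% or 50%, a 25% relative fall and rho from 0.3 to 0.8 (capped at its feasible maximum), the interval is 1.06 to 1.19 times too wide with 100 controls and 37 shared. It is 1.09 to 1.35 times too wide with 272 controls and 100 shared.

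**7. What it could do to the criterion, under one reading.** Suppose the interval must show a reduction of more than 25%. Take 50% prior use, a true 40% reduction (to 30%), 100 controls, 37 shared and rho = 0.5.
- SE of the log risk ratio without the covariance: √(0.5/50 + 0.7/30) = 0.183.
- Covariance term: 2 × 37 × 0.5 × √(0.25 × 0.21)/(10,000 × 0.5 × 0.3) = 0.0057. Correct SE: √(0.0333 − 0.0057) = 0.166.
- The margin is ln 0.75 − ln 0.60 = 0.223. Chance of passing as planned: Φ((0.223 − 1.645 × 0.183)/0.166) = 32%. With the covariance: Φ((0.223 − 1.645 × 0.166)/0.166) = 38%.

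**The case against.** Several points on the other side are sound.

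- **Separate people.** A reader might infer from N = 300 that the plan declares the groups to be distinct people. It does not say so. The figure is a sum of three hundreds, Section 3 gives 100, and Section 9.5 calls the data pre-post. What stands is narrower: no patient-level term is named, and the totals conflict.
- **Full pairing.** The pre-post label might suggest that the 100 controls are the same 100 people. The excess would then be far larger: at m = 100 and n1 = 100 the ratio is 1/√(1 − 0.7) = 1.83. But Section 9.5 sets the four clinics overall against enrolled PLWD, so the documents do not support that reading.
- **Certain overlap.** The overlap is possible by rule, not shown. With 100 randomly drawn controls, only some 22 to 37 people are shared under the assumptions above, and no section says that selection is random. If the overlap is small, so is the error.
- **No identifier.** Section 11.3 already provides a participant ID for data leaving the site. What it lacks is a statement that the ID is the same for a person's control-window and intervention-window records.
- **Harder to pass.** A too-wide interval makes the criterion harder to meet if the interval must exclude decreases of 25% or less. If its lower limit need only reach beyond a 25% decrease, a wider interval makes passing easier. The wording allows both.
- **Bigger problem elsewhere.** Participants are handed over by providers for behavioral concerns, while controls qualify on diagnosis alone. That can bias the estimate itself. It is a separate issue and does not make the interval correct.

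Section 9.5 also concedes limited power. That caveat carries little weight here, because the same section uses the interval as a condition for proceeding.

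**Conclusion.** The concern holds in a conditional form. The control rule admits later enrollees, and Section 9.5 names only within-clinic correlation. To the extent that people are in both sets, the 90% interval for the second go criterion therefore leaves out their within-person covariance and is usually too wide. Under 40% use and a correlation of 0.5 to 0.8, the standard error is too large by between 6% and 32% across the four overlap cases. These figures rest on assumed use, correlation and overlap, on a 2021 count of patients over 65, and, for the 22 and 37, on random selection of controls.

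The documents do not support saying that the interval is wrong by a known amount, or that the go decision is biased in a known direction.

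**What to change.** 1. In Section 4.1, state that a PLWD may be in both the control and the DICE sets.
2. In Sections 10.3 and 11.3, specify that the participant ID is the same for a person's control-window and intervention-window records, assigned at UCD before de-identification.
3. In Section 9.5, estimate the marginal pre-post difference or ratio in proportions with patient-clustered standard errors and clinic as a fixed effect. If a patient random intercept is used instead, standardise to marginal proportions before applying the second criterion. The need is real: a fall from 40% to 30% is a marginal odds ratio of (0.30/0.70)/(0.40/0.60) = 0.64, but a patient-specific one of about 0.23 at a correlation of 0.7. The implied intercept SD is near 5, with at most two records per person to estimate it.
4. Report the number of people in both sets.
5. Reconcile N = 300 (Section 9.1) with N = 100 (Section 3), and all PLWD with 100 controls, and state N as distinct people. Clarify which way the lower limit in the second criterion is to be read.

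The cost is a linked ID in the extract and a changed variance estimator; no new patients or data are needed. The ID has to be settled before extraction. None of this addresses the difference between referred participants and controls drawn from all PLWD, which needs its own remedy.
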